## Protocol and Planned Statistical Analysis

### Background and Rationale

Humans spend approximately a third of their lifetime sleeping. Sleep is viewed as a state of energy conservation and replenishment of energy storage. Human behaviors and certain pathological conditions may affect this important physiological process, resulting in sleep disturbances, including insufficient sleep, poor sleep quality and obstructive sleep apnea (OSA). There is a large body of evidence from human experimental as well as observational studies linking sleep disturbances to abnormal glucose metabolism and diabetes risk.

Insufficient sleep has been linked to reduced insulin sensitivity and increased risk of type 2 diabetes, both in laboratory studies in healthy humans and in epidemiologic studies. A causative role of partial sleep restriction in promoting alterations in glucose metabolism was first established in 1999(1). Intravenous glucose tolerance testing (IVGTT) following sleep restriction to 4 hours per night(h/night) for 5 nights resulted in a 24% decrease in insulin sensitivity as well as a 30% decrease in the acute insulin response to intravenous glucose(1,2). Multiple cross sectional epidemiologic studies have indicated that short sleep duration (usually < 6 h/night) is associated with increased impaired glucose tolerance and diabetes risk(3). A recent meta-analysis including 7 of these 10 studies (total 107,756 participants concluded that short sleep ( $\square$  5-6 h/night) predicts the development of type 2 diabetes with a pooled relative risk (RR) of 1.28(4). There are only a few studies examining the impact of insufficient sleep on glycemic control in patients with established type 2 diabetes. A questionnaire survey study of 161 African Americans with type 2 diabetes found that 3 hours of perceived sleep debt per day (i.e. a self-report of insufficient sleep duration) predicted a HbA1c level of 1.1% above the median(5). The magnitude of this difference is comparable to the effect size of several FDA-approved diabetes medications. Recently, a large cross sectional study of 4,870 Japanese participants revealed a U-shaped relationship between sleep duration and glycemic control, with higher HbA1c levels in patients with self-reported sleep duration <5.5 h/night and  $\square$  8.5 h/night compared to those with 6.5-7.4 h/night (6). These data support a role of sleep duration on glycemic control in patients with type 2 diabetes. However, the assessments of sleep duration in these studies were done subjectively i.e. by questionnaires. The only study which assessed the relationship between glycemic control (HbA1c) utilizing objective sleep measurement by actigraphy revealed that only sleep fragmentation, but not sleep duration, was associated with higher HbA1c level (7).

In addition, other aspects of sleep disturbances have also been shown to affect glucose control in patients with type 2 diabetes, including poor sleep quality(8) and the severity of untreated OSA (9). Therefore, the independent role of sleep duration and glycemic control requires further investigation. Whether the relationship extends to those with prediabetes is unknown. We hypothesized that prediabetes patients with short sleep duration, as measured objectively, will have worse glucose tolerance than those with normal sleep duration.

GLP-1 is an important incretin hormone which plays a role in regulating postprandial glucose excursion and appetite regulation. The role of sleep in GLP-1 regulation was explored in a few experimental studies in healthy human. Sleep restriction to 4 hours per night in healthy participants resulted in lower GLP-1 levels in the afternoon in women (10). In addition, total sleep deprivation in healthy participants resulted in a delayed GLP-1 response to breakfast (11). Sitagliptin treatment for 12 months in patients with type 2 diabetes resulted in 0.6% decrease in HbA1c as well as improved sleep quality as assessed by questionnaire (12). The role of GLP-1 response in patients with prediabetes who are short sleepers has not been explored. We hypothesize that those with chronic short sleep will have a lower or delayed GLP-1 response to meal compare to those with normal sleep duration. If this is proven, GLP-1 therapy may especially be effective in improving glycemic control in patients with abnormal sleep. Since the current proposed study is exploratory in nature by means of association, future interventional trial will be needed to show the causal relationship between GLP-1 and sleep.

Therefore, the aims of the current study are to explore the relationship of sleep duration and glucose tolerance in patients with prediabetes, as well as the effects of chronic short sleep duration on GLP-1 response to meals in these patients

**Objectives & Hypotheses:**

1. To determine the independent role of sleep duration on glucose tolerance in patients with prediabetes.
2. To determine if patients with prediabetes with short sleep have delayed or reduced GLP-1 response to a meal

**Hypothesis**

1. Prediabetes patients who have insufficient sleep will have worse glucose tolerance than those with normal sleep duration.
2. Prediabetes patients with short sleep will have a delayed or reduced GLP-1 response to a standardized meal

**Study Design/Population/Method**

The study has three components;

Step 1: Questionnaire study of 600 patients with prediabetes. The questionnaires will capture subjective sleep measurements and eating habits.

Step 2: Participants ages 40-65 reporting short sleep duration ( $\leq 6$  h/night) and normal sleep duration (7-8 h/night) will undergo objective sleep measurements including sleep duration, sleep quality and obstructive sleep apnea. This step will serve as a screening for step 3 (expected N= 80).

Step 3: Study to compare GLP-1 response to standard mixed meal test in patients with chronic short sleep and those with normal sleep duration. (n= 31 in each group).

**STEP 1:****Inclusion Criteria:**

1. Patients with prediabetes (HbA1c 5.7-6.4% or history of fasting plasma glucose 100-125 mg/dl) who receive medical care at Ramathibodi Hospital
2. Age 18 or older
3. Can understand Thai (speaking, listening and reading)
4. Agree to participate by written informed consent

**Exclusion criteria:**

1. Those who depend on others for feeding (such as stroke patients)
2. Shift workers
3. History of congestive heart failure or low ejection fraction
4. Chronic obstructive pulmonary disease, end stage renal disease or chronic liver disease (AST or ALT  $> 3$  times the upper limit of normal)
5. Use of medications: opioids/ narcotics, alpha blockers (prazosin, doxazosin, terazosin), clonidine, methyldopa, nitroglycerin
6. Patients with permanent pacemaker
7. History of previous stroke

[figure not shown]
**STEP 2:**

Participants age 40-65 who completed step 1 and were not taking diabetes medications will be invited to participate if they reported sleep duration  $< 6$  h/day, or normal sleep duration (7-8 h/day). They will undergo objective sleep assessments

**STEP 3:**

Participants who complete step 2 and are confirmed to have short sleep duration and normal sleep duration by objective assessments will undergo a mixed meal test with measurements of GLP-1, glucose and insulin.

## Study Procedures/Study Flowchart

### STEP 1

After informed consents are obtained, the participants will be interviewed regarding their medical history and sleep schedules on weekdays and weekends, as well as other aspects of sleep, mood and dietary habits. Standardized questionnaires will be utilized, including Morningness-Eveningness questionnaire (13) Pittsburg Sleep Quality Index to assess sleep quality (14), Berlin Questionnaire to assess risk of sleep apnea(15), depressive symptoms (CES-D)(16), Epworth Sleepiness Scale to assess daytime sleepiness (17), and review of dietary intake in the past 24 hours (24 hour food recall).

Medical records will be reviewed to collect data regarding medication use.

Weight, height, hip and waist circumference as well as neck circumference will be measured.

Blood sample will be obtained for hemoglobin A1c levels within 6 months of an interview if not done in the prior 6 months. Additionally, blood sample will be saved for possible further genetic and metabolic analyses.

### STEP 2

Those between ages 40-65 years who reported short sleep (≤6h/day) and normal sleep (7-8 h/day) will undergo objective sleep measurements as follow. Expected participants = 80

Participants will wear Actiwatch (Respironics, USA) at home for 1 week. Actiwatch is a small, watch-like device which can measure sleep timing and quality, daytime activities as well as light exposure.

Participants will wear the device on their non-dominant wrist and instructed not to wear clothes which sleeves may cover the watch. The device is water resistant.

During this week, the participants will keep a record of their sleep schedules and dietary intake.

On the last morning of actiwatch wearing, participants will collect overnight urine for urine melatonin measurements. They will fast after midnight and return to the hospital to have blood sample taken for fasting glucose and insulin, as well as return the actiwatch device.

The participants will bring the device, Watch PAT 200(18), to wear overnight at home. This device will assess the presence and the severity of sleep apnea (Apnea Hypopnea Index). This non-invasive device is shaped similar to a large watch which the participants will wear on their non-dominant wrist. There will be two probes connecting the device to their fingers to measure peripheral arterial tone and oxygen saturation. The participants will wear the device before going to bed, remove it upon awakening and return the device to the investigators in the morning.

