### **Statistical Methods**

STEP 1 and 2:

Sleep variables from questionnaires (subjective) and actigraphy/WatchPAT (objective) including sleep duration, sleep quality and sleep apnea will be analyzed to explore their relationship with HbA1c, and when available, fasting glucose and insulin levels. Bivariate analysis will be used. To identify the independent sleep predictor of glucose tolerance status, multivariate regression analysis will be employed.

STEP 3:

Area under the curve of GLP-1 and its peak response will be compared between short and normal sleepers.

Power/Sample Size:

STEP 1: The sample size of 600 was selected to follow a rule of 10 participants for each variable in the multivariate regression analysis. Predictors of HbA1c include age, sex and BMI. Sleep predictors will include sleep duration, quality and sleep apnea risk. In addition, the sample size was chosen to ensure adequate recruitment of short sleepers (based on prevalence of 20-25%) into STEP 2 and 3.

STEP 2: The sample size of 80 in step 2 was chosen to ensure adequate recruitment for STEP 3 which requires 62 participants, with a 75% concordance rate of self-reported and objectively measured sleep duration

STEP 3: Based upon a sample size of n=31 patients per group, this study has 80% power to detect a 35% difference in the peak time of GLP-1 between groups GLP-1 level with a 10% drop out rate. This calculation is based on data of a previous study of acute sleep deprivation and GLP-1 response (11).

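### HbA1c may be up to 6 months from the sleep interview, with no limit on its gap from actigraphy; adding HbA1c to the existing Step 2 fasting sample is a cheap improvement

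*Combined protocol and SAP*

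**What the plan says.** All places are in the combined protocol and SAP.

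- **HbA1c timing** (Study Procedures/Study Flowchart, STEP 1): "Blood sample will be obtained for hemoglobin A1c levels within 6 months of an interview if not done in the prior 6 months". An existing value up to 6 months old is accepted; otherwise a new one is taken within 6 months of the interview.
- **Stored blood** (same section): "Additionally, blood sample will be saved for possible further genetic and metabolic analyses". The text does not say when this sample is drawn, or whether it is separate from the HbA1c sample.
- **Objective sleep** (Study Procedures/Study Flowchart, STEP 2): "Participants will wear Actiwatch (Respironics, USA) at home for 1 week". WatchPAT is worn at home for one night. No maximum interval is given from the Step 1 interview, or from the HbA1c date, to either recording.
- **Step 2 blood** (same section), on the last morning of actigraphy: "They will fast after midnight and return to the hospital to have blood sample taken for fasting glucose and insulin". HbA1c is not on that list.
- **Analysis** (Statistical Methods, STEP 1 and 2): questionnaire and actigraphy/WatchPAT sleep variables "will be analyzed to explore their relationship with HbA1c, and when available, fasting glucose and insulin levels", first in bivariate analysis and then in multivariate regression. HbA1c is the only outcome named without a condition. The plan does not mention recording the HbA1c-to-sleep interval, adjusting for it, or testing sensitivity to it.

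**The concern.** Objective 1 asks whether sleep duration is independently related to glucose tolerance, and in Steps 1 and 2 HbA1c carries most of that question. If HbA1c and sleep are measured months apart, within-person change over the gap enters the analysis as noise, and a real association becomes harder to detect.

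The pairing matters most in Step 2. The Background justifies the study largely by the weakness of self-reported sleep, so objective sleep against HbA1c is a central comparison. Yet the 6-month limit is tied to the interview and not to the actigraphy week. A chart value already 6 months old at the interview is older still by the time of any later recording. Step 2 also has no stated margin to absorb a loss: its 80 participants were chosen to supply Step 3, not to power an HbA1c association.

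**Working it through.** **The plan's own figures.** No stated figure depends on when HbA1c is taken. Step 1's 600 is attributed to 10 participants per variable. The named predictors are age, sex, BMI, sleep duration, sleep quality and apnea risk, and 10 × 6 = 60; 600 would correspond to 60 variables. The lists are open-ended and no count is given, so 600 can be neither reproduced nor called wrong. Its second purpose is to yield short sleepers: 20–25% of 600 is 120–150. Neither argument gives an effect size for HbA1c.

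**Inputs.**
- From the documents: N = 600 (Step 1) and N = 80 (Step 2).
- Assumed: two-sided alpha of 0.05, and λ, the correlation between the HbA1c used and the HbA1c that would have been found at the sleep measurement. The documents give no HbA1c SD, no within-person stability of HbA1c or sleep, and no effect size, so λ is varied from 0.6 to 1.0.

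**Step A: reference correlation.** With concurrent HbA1c (λ = 1), the correlation detectable with 80% power by Fisher's z is

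r = tanh[(1.960 + 0.842) / √(N − 3)]

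- N = 600: tanh(2.802 / √597) = 0.114
- N = 80: tanh(2.802 / √77) = 0.309

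These are reference points, not effects expected by the plan.

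**Step B: effect of the gap.** If the extra HbA1c variation is unrelated to sleep, the observed correlation is λ × r, and

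power ≈ Φ[atanh(λr) × √(N − 3) − 1.960]

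The sample needed to restore 80% power grows by about 1/λ².

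| λ | Power, N = 600 | Power, N = 80 | Sample multiplier 1/λ² |
|---|---|---|---|
| 1.0 | 80% | 80% | 1.00 |
| 0.95 | 76% | 76% | 1.11 |
| 0.9 | 71% | 71% | 1.23 |
| 0.8 | 61% | 60% | 1.56 |
| 0.7 | 50% | 49% | 2.04 |
| 0.6 | 39% | 38% | 2.78 |

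Worked row, λ = 0.8 and N = 600: observed r = 0.8 × 0.114 = 0.091; 0.091 × √597 is about 2.24; 2.24 − 1.96 = 0.28; Φ(0.28) is about 0.61.

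**Step C: slope or only precision?** A simulation of 2,000,000 records with a true standardized slope of 0.20 separated two mechanisms.

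| Mechanism | λ | Slope | Correlation |
|---|---|---|---|
| Random HbA1c change, sleep stable | 0.8 | 0.20 | 0.16 |
| Sleep changes between the dates | 0.8 | 0.16 | 0.16 |
| Random HbA1c change, sleep stable | 0.6 | 0.20 | 0.12 |
| Sleep changes between the dates | 0.6 | 0.12 | 0.12 |

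Random movement in the outcome widens the confidence interval and lowers power but leaves the regression slope alone. The slope shrinks only when the exposure itself moves.

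**The case against.** The strongest reply has four parts.

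1. **The loss may be small or nil.** The study concerns chronic short sleep. If habitual sleep and HbA1c are both stable over a few months, λ is near 1: power falls only to 76% at 0.95, and not at all at 1.0. A single λ for everyone is also a simplification, because individual intervals can run from 0 to 6 months in Step 1 and their distribution is unknown. This stands, and is why no single size can be given.
2. **Step 2 has concurrent glycaemic outcomes.** Fasting glucose and insulin are drawn on the last actigraphy morning and are named in the analysis. Step 2 also invites only people not taking diabetes medication, which removes one source of HbA1c drift. This stands as partial mitigation. HbA1c is nonetheless analysed against objective sleep. The serial glucose and insulin of Step 3 do not fill the gap, because the Step 3 statistical paragraph compares only GLP-1.
3. **The study is exploratory.** The Background describes it as associational and leaves causal questions to a later trial. This stands: a same-day sample would still be cross-sectional, so the case rests on precision and not on temporal order.
4. **The window may save a blood draw in Step 1.** This also stands. A reader might infer from the stored sample that blood is taken from everyone at the interview, so that the window saves nothing. The text does not say so: the stored blood could be part of the HbA1c sample, and a new HbA1c sample may itself come months after the interview. Only in Step 2 is a draw at the sleep contact explicit.

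**Conclusion.** The point holds as a cheap improvement. HbA1c may be up to 6 months before or after the Step 1 interview, and its distance from the Step 2 sleep recordings has no stated limit. The likely cost is precision and power. Across an assumed λ of 0.6 to 1.0, power for a correlation otherwise detectable with 80% power is about 38% to 80%. The lower end is the edge of an assumed range, not an estimate.

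Two stronger readings are not supported. The first is that the association is necessarily biased toward zero: a linear slope is attenuated only if sleep changes between the dates, and the documents say nothing about whether it does. (Systematic change after an earlier HbA1c, such as a lifestyle change, could move the estimate either way.) The second is that HbA1c and the interview can be 12 months apart. The window spans 12 months across participants, but no one's HbA1c should be more than 6 months from their own interview.

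**What to change.** - **Study Procedures, STEP 2:** add HbA1c to the fasting sample already drawn on the last actigraphy morning. In Statistical Methods, state that this value is used in all actigraphy and WatchPAT analyses.
- **Study Procedures, STEP 1:** record the HbA1c-to-interview interval in days, and state when the saved sample is drawn. If it is in fact drawn at the interview, assay HbA1c on it.
- **Statistical Methods, STEP 1 and 2:** repeat the main Step 1 model in participants with a short interval, for example within 3 months, as a prespecified sensitivity analysis.

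Cost: about 80 extra HbA1c assays in Step 2, with no new visit or venepuncture. Assaying Step 1 samples would add one test for each participant who would otherwise have used an existing value; that number is not in the documents. Recording the interval and running the sensitivity analysis take a little extra work and no extra blood.

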### **STEP 3**

After confirming the sleep duration by Actiwatch, both short and normal sleepers will undergo a 75-gram OGTT after an overnight fasting. Serum glucose, insulin and GLP-1 will be collected every 30 minutes for 3 hours. Expected participants in each group = 31

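### The Step 3 challenge is named as a mixed meal test in two sections and as a 75-gram OGTT in the procedures; if only the OGTT is given, the planned conclusion about a meal is not supported

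*Combined protocol and SAP*

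**What the plan says.** All references are to the combined protocol and SAP.

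**Sections that name a meal test.** Under Study Design/Population/Method, Step 3 is a "Study to compare GLP-1 response to standard mixed meal test in patients with chronic short sleep and those with normal sleep duration". The STEP 3 paragraph that follows the Step 1 eligibility criteria says that participants with confirmed sleep duration "will undergo a mixed meal test with measurements of GLP-1, glucose and insulin".

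**Section that names an OGTT.** Under Study Procedures/Study Flowchart, STEP 3, "both short and normal sleepers will undergo a 75-gram OGTT after an overnight fasting". The next sentence gives the sampling: "Serum glucose, insulin and GLP-1 will be collected every 30 minutes for 3 hours". No meal is mentioned there.

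**The question to be answered.** Background and Rationale hypothesises that "those with chronic short sleep will have a lower or delayed GLP-1 response to meal" and gives as an aim "the effects of chronic short sleep duration on GLP-1 response to meals in these patients". Objective 2 is "To determine if patients with prediabetes with short sleep have delayed or reduced GLP-1 response to a meal". Hypothesis 2 predicts a "delayed or reduced GLP-1 response to a standardized meal".

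**The analysis.** Statistical Methods, STEP 3, compares GLP-1 AUC and peak between the two sleep groups without naming the challenge. The Step 3 power statement takes its input from reference 11, which Background and Rationale describes as a study of the GLP-1 response to breakfast.

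**The concern.** The challenge is the stimulus that defines the Step 3 outcome. A GLP-1 AUC after a mixed meal and one after oral glucose are different quantities, and the document names both stimuli for what reads as one session. Two things are at stake.

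The first is conduct: a site team working from the design section would give a different test from a team working from the procedures. The second is interpretation: the procedures are the most operational text and the only one with sampling times. If they are what is carried out, Objective 2 and Hypothesis 2 will be answered with data on a stimulus they do not mention.

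**Working it through.** The point rests on comparing the text, so the Step 3 descriptions are set side by side.

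| Element | Study Design | STEP 3 eligibility text | STEP 3 procedures |
|---|---|---|---|
| Challenge | Mixed meal test | Mixed meal test | 75-gram OGTT |
| Group size | 31 per group | not stated | 31 per group |
| Entry | not stated in the Step 3 entry | after objective confirmation of sleep duration | after confirmation by Actiwatch |
| Analytes | GLP-1 | GLP-1, glucose, insulin | GLP-1, glucose, insulin |
| Sampling times | none | none | half-hourly over three hours |

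**Step 1: is it the same session?** Wherever two descriptions cover the same element, they agree on group size, entry condition and analytes. They conflict on the challenge. The natural reading is one session under two names.

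**Step 2: is there reconciling text?** No visible sentence says that two tests are done, that the OGTT replaces the meal, or that one label covers the other. The Step 3 analysis sentence names no challenge, so it cannot settle the matter. A figure following the Step 1 exclusion criteria is not shown in the text available for this review. Whatever it contains, the conflicting sentences would remain.

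**Step 3: what would the data describe if the procedures alone are followed?** GLP-1 is drawn in the OGTT session. The AUC and peak comparison is then a comparison of responses to oral glucose. It can be interpreted as such, but it does not answer a question about a meal.

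**Step 4: how many participants?** 2 × 31 = 62 expected. If the 31 is before the stated 10% drop-out (an assumption), 0.9 × 31 = 27.9 per group, or 55.8 (about 56) in total.

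**Step 5: does the conflict show that the sample size is wrong?** No. The plan states 31 per group for 80% power to detect a 35% difference in GLP-1 peak time. This cannot be reproduced, because no SD, alpha or sidedness is given. Assuming two-sided alpha 0.05 and about 28 evaluable per group, the detectable standardised difference is d = (1.960 + 0.842) × √(2/28) = 0.749. The implied CV is 0.35 / 0.749 = 0.467. With 31 evaluable, d = 0.712 and the CV is 0.492. The stated size is attainable at such a CV, and the document gives no figure to judge whether that CV suits a meal or an OGTT.

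**Step 6: how far would the two responses differ?** This cannot be computed. The document gives no GLP-1 figures for either challenge.

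**The case against.** The strongest reply is that little is lost. Both sleep groups have the same test under any single section, so the comparison between them is like-for-like. The harm is conditional on the procedures being followed alone. The protocol also describes itself as exploratory, and a two-test design cannot be excluded. Most of the text agrees on a meal, and one sentence departs from it.

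Much of this stands and limits the point: no bias and no loss of power is claimed, and what will be done is uncertain. It does not remove the point. The departing sentence is the one staff would carry out, and if two tests were intended, no section says so or gives the meal test a schedule.

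A reader might infer more than the document supports:

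- *That replacing the OGTT would leave Objective 1 without its glucose tolerance assessment.* Statistical Methods addresses glucose tolerance status under Steps 1 and 2, using HbA1c and, where available, fasting glucose and insulin. It plans no analysis of Step 3 glucose, so the choice of challenge changes no planned Objective 1 analysis. Whether those measures are adequate for that objective is a separate question.
- *That the OGTT is the wrong test.* The document supports only the conflict. The choice is the sponsor's.
- *That the power calculation fails because its source used breakfast.* If GLP-1 is measured on the OGTT, the stimulus is a further difference from the source study. That study already differs in studying acute rather than chronic sleep loss, and healthy men rather than people with prediabetes. None of this shows that 31 per group is wrong.

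**Conclusion.** The inconsistency is real and should be resolved. Confidence is high that the wording conflicts; it is not high on which test or tests will actually be given. If the OGTT alone is given, all Step 3 GLP-1 data (62 expected participants) describe the response to oral glucose, and a conclusion about the response to a meal is not supported. That rests on two assumptions: that the three descriptions refer to one session, and that the figure not shown does not state a two-test design. Even if the second assumption fails, the text still needs correcting, because the sections as written direct staff to different tests.

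**What to change.** 1. Reconcile the Step 3 entry in Study Design/Population/Method, the STEP 3 eligibility text and the STEP 3 procedures. State which test or tests are given (or were given, if Step 3 has started), that they are applied identically in both groups, and on which one GLP-1 is measured. Attach the sampling schedule to that test.
2. Make Objective 2, Hypothesis 2, the Step 3 sentence in Statistical Methods and the eventual conclusion name the same challenge.
3. If GLP-1 is measured on the OGTT, restrict the conclusion to the response to an oral glucose load, and note in Power/Sample Size that the input comes from a breakfast study.
4. If Step 3 has already started, date any rewording and label it as a change to the objective, so that it does not read as the question set at the outset.

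The cost is an amendment to the objective or to the procedure text, with no added patients. It is more than an editorial correction, since either the stated question or the stated procedure changes.

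### Step 3 names serum as the GLP-1 specimen and does not specify inhibitor, cooling, time to spin or GLP-1 form, so an assay of intact GLP-1 would be exposed to breakdown during clotting

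*Combined protocol and SAP*

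**What the plan says.** Study Procedures/Study Flowchart, STEP 3, is the only place that names a specimen for GLP-1: "Serum glucose, insulin and GLP-1 will be collected every 30 minutes for 3 hours". As written, serum governs all three analytes. The shorter description of STEP 3 under Study Design/Population/Method says only that participants "will undergo a mixed meal test with measurements of GLP-1, glucose and insulin".

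For the analysis, Statistical Methods states: "Area under the curve of GLP-1 and its peak response will be compared between short and normal sleepers". No other Step 3 outcome is listed there. The hypothesis being served is "Prediabetes patients with short sleep will have a delayed or reduced GLP-1 response to a standardized meal".

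The sample-size paragraph begins "Based upon a sample size of n=31 patients per group" and claims "80% power to detect a 35% difference in the peak time of GLP-1 between groups", "with a 10% drop out rate". It points to an earlier acute sleep-deprivation study for its inputs and gives no standard deviation, significance level or sidedness.

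The document contains no collection tube, enzyme inhibitor, temperature, time to spin, storage condition, assay or GLP-1 form, and it cites no laboratory manual.

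**The concern.** Serum has to clot before it is spun. Intact GLP-1 is cleaved in blood by dipeptidyl peptidase-4 (DPP-4), and in an untreated tube that cleavage can continue during clotting. This is general laboratory knowledge, not a statement in the documents, and it is used here as an assumption. On that basis, the one specimen the plan names is poorly suited to intact GLP-1.

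The form assayed is a second gap. Intact GLP-1 reflects active hormone in the circulation. Total GLP-1 includes the cleaved product and is closer to what was secreted. A lower AUC means different things under the two forms, and the plan does not say which is meant. This gap exists even with perfect sample handling.

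At stake are the precision and the interpretation of the Step 3 comparison. GLP-1 AUC and peak are the only outcomes compared, with about 28 evaluable participants per group. Intact hormone lost in the tube cannot be recovered later.

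**Working it through.** **1. The plan's own figure.** The 31 per group cannot be reproduced, because standard deviation, significance level and sidedness are not given. It can be solved backwards, assuming a two-sided 5% level.

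- Evaluable per group: 31 × 0.9 = 27.9, about 28.
- Normal approximation: d = (1.960 + 0.842) × √(2/28) = 0.749. A 35% difference then implies a coefficient of variation (CV) of 0.35/0.749 = 46.7%.
- t-test: d = 0.762, so the CV is 0.35/0.762 = 45.9%.
- Going forward from a CV of 46.7%: 28 evaluable per group, which becomes 28 × 1.1 = 30.8 (31) or 28/0.9 = 31.1 (32) with dropout.

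So 31 is plausible, but only for a standard deviation the plan does not state.

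**2. Fraction of intact GLP-1 left after clotting.** Assumptions: exponential loss, 45 minutes to spin, and in-tube half-life h of 30 to 240 minutes. Fraction left = 0.5^(45/h).

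**3. Extra noise from variable time to spin.** Assumptions: one handling time per participant, normal, with standard deviation s of 10 or 15 minutes.

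- CV of the loss factor: c = √(exp((s × ln 2 / h)²) − 1).
- Combined CV: √((1 + 0.459²)(1 + c²) − 1).
- Power is from the t-test with 28 per group and a 35% difference in concentration.

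Example, h = 30 and s = 15: c = 0.357; combined CV = √(1.211 × 1.128 − 1) = 0.604; d = 0.35/0.604 = 0.579; power 57%.

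| Half-life (min) | Intact left at 45 min | Power, s = 10 | Power, s = 15 |
|---|---|---|---|
| 30 | 35% | 69% | 57% |
| 60 | 59% | 77% | 73% |
| 120 | 77% | 79% | 78% |
| 240 | 88% | 80% | 80% |

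In the last row the loss is under one percentage point. These are upper-end losses for AUC, since variation between a participant's tubes would partly average out (seven tubes at 30-minute steps over 3 hours, counting time 0).

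**4. What the table does not cover.** It treats the 35% as a difference in level, while the plan's power statement names peak time. If every sample of a participant is multiplied by the same factor f, the highest sample stays highest and peak time does not move. Peak time would be disturbed only by loss that varies between tubes, or by values pushed to the assay floor. Neither was quantified.

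**5. Bias.** If loss is the same in both groups, the ratio of group means is unchanged: (f × short)/(f × normal) = short/normal. Bias appears only if handling differs. If one group's tubes waited 10 minutes longer on average, its apparent level would be lower by 1 − 0.5^(10/h), which is 21%, 11%, 6% or 3% at the four half-lives.

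**The case against.** The strongest reply is that the plan is silent on laboratory detail generally. It gives no tube or processing detail for HbA1c, fasting insulin or urine melatonin either. The word serum may be loose drafting aimed mainly at glucose, and the laboratory may already use treated tubes. That stands in part. A reader might infer that GLP-1 will be collected without an inhibitor, but the documents do not say so. They only fail to specify one. For GLP-1, however, the plan goes beyond silence: it names a specimen, and followed literally that specimen is a problem for an intact assay.

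A reader might also infer that Step 3 loses its stated 80% power. The documents do not support that. The power statement concerns peak time, which proportional loss does not move, and the half-lives and handling times in the table are assumptions.

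Nor does it follow that a null result would be indistinguishable from sample loss. The hypothesis covers delay as well as reduction, and the delay part is largely robust. Group bias would require handling to differ between short and normal sleepers, and nothing in the documents suggests that it does.

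Finally, one might argue that total GLP-1 has to be primary because the hypothesis is about secretion. The objectives and hypothesis speak of a response, and the rationale refers to control of glucose after meals and to possible GLP-1 therapy. Either form could serve. What matters is that the choice is stated, and a total assay would itself remove most of the breakdown concern.

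**Conclusion.** The point holds as a conditional one. The plan names serum for GLP-1 and specifies neither the handling nor the form assayed. If intact GLP-1 is measured in untreated serum, AUC and peak height would be lowered and made noisier.

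The size cannot be fixed from the documents. Under the assumptions shown, power for a concentration endpoint that starts at 80% ranges from about 57% to almost no loss, depending mainly on the in-tube half-life. With a total-GLP-1 assay the effect is much smaller. The figures illustrate sensitivity and do not re-estimate the study's power.

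The undefined form of GLP-1 needs none of these assumptions: without it, a reduced AUC cannot be read as either less active hormone or less hormone secreted. Overall this is a cheap improvement to make before sampling, and it does not show that the Step 3 comparison is invalid.

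**What to change.** - **Study Procedures/Study Flowchart, STEP 3.** Limit serum to glucose and insulin. Collect GLP-1 as plasma in chilled EDTA tubes containing a DPP-4 inhibitor, spun within one fixed time that is the same for all participants, then frozen.
- **Statistical Methods, STEP 3.** State before sampling whether intact or total GLP-1 is used for AUC and peak, name the assay, and limit the conclusion to that form.
- **If serum has already been drawn.** Use a total-GLP-1 assay validated for serum and conclude on total GLP-1 only.

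The cost is about one sentence in each section, and a different tube and slightly more processing at draws already planned. No visits, procedures or participants are added.
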